**Table 3: Number of participants per arm for 1-sided alpha of 0.025 and power of at least 85%.**

True Hb Mean Difference (treated – control)	Sample size (per group)
0	65
-0.1	80
-0.2	101
-0.3	131
-0.4	179

## 2.5 Framework and statistical principles

The qualitative study that precedes the trial will be used to guide implementation and evaluation of the larger study at the UH3 Phase, including identifying barriers and recommendations for using iron supplementation and nutritional counselling to increase the blood donor pool. Moreover, qualitative findings resulting from focus groups to be conducted at the end of the trial and key informant interviews will be used to guide the planning, implementation, and evaluation of the UH3 phase.

The following general principles will apply to this pilot. All confidence intervals (CIs) are 2-sided and at the 95% level and hypothesis tests are 2-sided at the 5% significance level unless otherwise specified. Percentages, means, medians and quartiles will be rounded to one significant digit. P-values will be given to 2 significant figures. Version

9.3 (or later) of SAS and/or version 3.5 (or later) of R will be used to conduct the analysis and generate tables and figures.

Descriptive statistics for enrolment rates over time and the proportion of participants completing the 6-month study visit will be assessed by treatment group. Those statistics will be used to determine the feasibility of the larger study (UH3) and may lead to changes in how consent, enrolment, and follow-up are conducted.

**Cut-date for interim reviews:** Analysis data sets will be frozen (locked) several days (or weeks) prior to the review date, to allow the statisticians time to prepare a consistent report. The cut-date may be earlier than the date of the data freeze, to allow for additional time for the reporting of events.

## 2.6 Interim analyses and DSMB reviews

### Goals of the interim reviews:

Protect the safety of study participants.

Review the conduct of the trial.

Reviews will be timed according to the recommendations of the DSMB and study leadership.

**Review meetings** will typically consist of an executive session (optional; closed), open session, closed session, and a second open session to give feedback to study leadership (optional).

### Open report to the DSMB

The open reports will contain:

A synopsis of the trial design and current status of the study.

Responses of the study team to DSMB requests.

A summary prepared by the study leadership.

Data summaries for

- Key Informant Interviews
- Anaemia Deferment Study
  - Baseline characteristics overall and stratified by consent into the Iron Supplementation Trial
- Prevalence of ID and IDA Study
  - Screening, baseline characteristics
- Iron Supplementation Trial
  - Screening, enrolment, eligibility violations, protocol deviations, and baseline characteristics overall.
- FGD

Summary reports for data completeness and study conduct (pooled across treatment groups for the Iron Supplementation Trial)

New literature relevant to the trial and recommendation as to whether it affects the trial conduct or design, will also be provided to the DSMB by the study leadership. This is usually included with the open report but may be shared confidentially if needed.

All data summaries in the open report involving safety or follow-up data will be pooled across the treatment arms for the Iron Supplementation Trial. The open reports will be prepared by a DCC statistician.

While the study is ongoing, summaries and comparisons by treatment group are restricted to the confidential closed report to the DSMB. Additionally, all summaries of follow-up data other than the data completeness and study conduct reports will be restricted to the confidential closed report. On a case-by-case basis, other pooled follow-up data may be provided if explicitly approved by the DSMB.

### **Closed report to the DSMB**

The closed reports for a full review will contain:

- Specific data summaries requested by the DSMB or study leadership.
- Data summaries for the trial in the open report presented by treatment group.
- Safety and follow-up for the trial (including adherence to iron supplementation) overall and by treatment group.
- Listings of grade 3, 4 adverse events (AEs) events and serious adverse events (SAEs).
- Analysis of the efficacy of the intervention.

The closed reports will be prepared by a DCC statistician with access to the full data set.

## **2.7 Timing of final analysis**

The primary study report will be written after enrolment and follow-up for the primary outcome of the Iron Supplementation Trial is completed or the study is stopped by the sponsor after recommendation by the DSMB (e.g., safety, futility or efficacy reasons).

## **3 Study Population**

### **3.1 Eligibility**

#### **Inclusion Criteria**

There are 3 components of the quantitative study (observational study of deferral, observational study of the prevalence of ID and IDA, and the parallel groups trial of iron supplementation) with slightly different inclusion and exclusion criteria, hence we indicate which criteria apply to which component of the study below.

Items 1-3 are required for the observational study of deferral, items 1-4 are required for the observational study of the prevalence of ID and IDA and items 1-6 are required for the trial. Only participants who meet ALL the following inclusion criteria will be eligible for the trial:

- 1) Males or females aged between 17 and 60 years who weigh at least 50kg.
- 2) Pass pre-donation screening using the NBSG standardised donor screening questionnaire for medical conditions and lifestyle risks for transfusion transmissible infections (TTIs) (Appendix 5).

- 3) Vital signs must meet the NBSG requirement for blood donation: systolic and diastolic blood pressures between 90-140 mmHg and 60-90 mmHg, respectively; pulse rate between 50-100 bpm; non-contact forehead temperature not exceeding 37.5°C; meeting acceptable requirements for skin lesions, needle marks and physical appearance.
- 4) Must be willing and able to give study consent or assent.
- 5) Intend to remain in the study location/site during the entire length of the study.
- 6) Voluntary non-remunerated blood donor

### **Exclusion Criteria**

There are no additional exclusion criteria for the observational study of deferral, items 1-2 are required for the observational study of the prevalence of ID and IDA, and items 1-5 pertain to the clinical trial. All persons who meet ANY of the following exclusion criteria will be excluded from participating in the clinical trial.

- 1) Persons who have used iron supplementation within the past one month.
- 2) Participant reports having previously donated blood.
- 3) Evidence for a TTI at screening among those who successfully donated.
- 4) Evidence of malaria (malaria rapid test at screening) and helminthic infections from specimens obtained at screening.
- 5) Participants who have Hb <10g/dl at screening.

Potential donors who are found to have Hb < 10g/dl at screening will be referred for further evaluation and care by a haematologist. Any trial participant found to have Hb < 10g/dl at any follow-up visit will be referred for evaluation by a haematologist.

Since participants will only be tracked if they meet eligibility criteria for the study, the consolidated standards for reporting trials (CONSORT) diagram will start with those who consented to the Iron Supplementation Trial. Due to the complexity of the interrelated components of the study, multiple diagrams may be necessary for an accurate characterization of enrolment and follow-up.

For the open report, the following enrolment and eligibility summaries will be provided for those who consented to the Iron Supplementation Trial:

Screening and enrolment over calendar time: plot by day and week, cumulative and increments.

Consented but unable to recontact: number (%).

Eligibility: number (%) and reasons for eligibility violations.

For the Iron Supplementation Trial: Number (%) eligible at screening pending laboratory results and not eligible for enrolment visit with % for each reason (e.g., expiration of laboratory result (timing of expiration and by which laboratory result), Hb < 10 g/dL, Malaria, Helminthes, TTI).

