### **Secondary Objectives**

- To determine changes in haemoglobin in blood donors over a 6-month period.
- To determine the impact of iron supplementation on the change in haemoglobin.
- To estimate the prevalence of ID and IDA in prospective first-time blood donors.
- To determine the factors associated with ID and IDA among prospective blood donors.
- To determine the prevalence of malaria or adverse events among the prospective first-time blood donors.
- To identify the barriers and facilitators of repeat donation and the use of dietary and iron supplementation interventions to address ID and/or anaemia among blood donors.
- To determine feasibility of the intervention, through documenting implementation fidelity, intervention adaptation, and intervention strengths and weaknesses.
- To understand participant and key informant acceptance of the intervention.
- To develop and implement key strategies aimed at increasing the blood donor pool.

- To compare haemoglobin levels as determined by copper sulphate versus automated haematology analyser.

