### 3.4 Baseline characteristics

Baseline characteristics for those who enrol in the trial will come from information collected on the screening and enrolment forms. The only characteristics captured for those in the anaemia deferment study are age, sex, if the person has previously donated, and the type of donation (i.e., replacement/family or voluntary). For those in the study of ID/IDA information on abnormal peripheral blood film, malaria, haemoglobin, ferritin, and TTI status will also be obtained. Additional information will be available for those in the trial. For the open report, baseline characteristics will be summarized pooled across the two treatment groups and presented separately for those in the anaemia deferment study, the ID/IDA study, and the trial. Note that these study populations are related as follows: everyone in the trial is in the ID/IDA study, and everyone in the ID/IDA study is in the anaemia deferment study. Note that someone who consents to the trial but is found to have levels of haemoglobin that are too low at screening will participate in the ID/IDA study but will not participate in the trial.

For the closed report, baseline characteristics will be summarized by treatment group for the Iron Supplementation Trial.

The following baseline characteristics will be summarized with counts and percentages for binary and categorical variables, medians and quartiles for continuous variables and ordinal variables when available for each of the 3 components of the study.

Demographics:

- Age: summary as continuous variable.
- Sex.
- First-time donation status (Yes or No).
- Number of children (an integer equal or above 0).
- Marital status (6 options).
- Home situation (6 options).
- Main method of travel (private or public).
- Highest level of education completed (7 options).
- Employment category (8 options).
- Number of expensive, durable consumer items (an integer in the range 0-7).
- Ethnic background (6 options).
- Religion (5 options).

Screening laboratory results:

- Haemoglobin concentration.
- Plasma ferritin concentration.

- Malaria test results from a malaria rapid diagnostic test.
- Abnormal peripheral blood film results reported by type of abnormality (i.e., helminthic infection, malaria, neutrophilia, leucocytosis, and lymphocytosis).
- ID present
- IDA present.

Medical History:

- Diagnoses (19 options, select all that apply).

Nutritional History:

- Number of meals yesterday (4 options).

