## **7 Quantitative Data Analysis**

### **7.1 Cross-sectional study**

Analytical approaches to the analysis of data from the prevalence study will focus on univariate summaries but will also investigate risk factors for deferral. An exact

confidence interval for the probability of deferral will be computed using the method first described by Clopper and Pearson. Logistic regression will be used to assess risk factors for deferral. These risk factors will include age, sex, previous donation status and type of donor.

Since recruitment at donation events focuses on informing individuals who fail the copper sulphate test about the study, we expect that the proportions of those who are ID and IDA will be higher than the proportion among those attending a donation event. For this reason, we will estimate the level of ID and IDA overall by weighting the estimates within deferral strata by the observed probability of deferral based on the cross-sectional study of deferral (but restricted to first time donors, or voluntary first time donors depending on who enrolls into the ID/IDA study). To obtain 95% confidence intervals for the overall proportion of those who are ID and IDA we will use a Bayesian approach in which we sample the probability that first-time donors are deferred for low haemoglobin from its posterior distribution (which is a beta distribution) and we sample the probability of being ID and IDA conditional on deferral status from their posterior distributions (which will also be beta distributions). We can then combine these draws from the posterior distributions to obtain weighted estimates of the probability of being ID and IDA that will be consistent for these probabilities in the overall population. Risk factors for being ID and IDA conditional on the outcome of the copper sulphate test will be examined using logistic regression.

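### The post-stratified ID/IDA prevalence covers only donors without recent iron use, but SAP 7.1 presents it as consistent for all first-time donors

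*SAP*

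**What the plan says.** **Target.** The relevant secondary objective (SAP 1.2, Secondary Objectives) is "To estimate the prevalence of ID and IDA in prospective first-time blood donors". It has no iron-use qualifier.

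**Who is measured.** In SAP 3.1, Exclusion Criteria, "items 1-2 are required for the observational study of the prevalence of ID and IDA". Item 1 is "Persons who have used iron supplementation within the past one month"; item 2 is previous donation. The Protocol's Exclusion Criteria apply the same rule.

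**Who supplies the weights.** In the same SAP section, "There are no additional exclusion criteria for the observational study of deferral". SAP 7.1 takes the deferral probability from that study, "restricted to first time donors, or voluntary first time donors depending on who enrolls into the ID/IDA study". SAP 3.4 says "The only characteristics captured for those in the anaemia deferment study are age, sex", followed by previous donation and type of donation. Iron use is not on the list.

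**What is claimed.** SAP 1.2, Stratification and Sampling, calls the proportions within copper sulphate strata unbiased. SAP 7.1 describes the weighted estimates as ones "that will be consistent for these probabilities in the overall population".

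**The concern.** SAP 7.1 accepts that the weights must describe the same people as the ID/IDA sample, since it restricts them to first-time (or voluntary first-time) donors. That matches exclusion 2 and leaves exclusion 1 unmatched. Weighting by copper sulphate result corrects for over-approaching donors who fail the test. It does nothing about a group removed from both strata.

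Recent iron users are a group whose ferritin and haemoglobin could well differ from other donors'. If they do, a prevalence reported for all first-time donors is shifted by an amount that the posterior interval does not contain and that a larger sample does not reduce. As planned, the shift may also be impossible to bound. The SAP tracks only people who meet eligibility criteria and starts its CONSORT diagram at consent, and the Protocol records screen-failure reasons only after a consent form is signed. Users turned away before consent might leave no count.

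**Working it through.** **1. The plan's own precision.** SAP 2.4, Table 2, uses 1.96 × √(p(1 − p)/n). With n = 292 and p = 0.2, 0.3, 0.4, 0.5 this gives 0.046, 0.053, 0.056 and 0.057, as printed. No stated figure is wrong; the problem is structural.

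**2. What is estimated.** Let q be the probability that a first-time donor fails copper sulphate (users and non-users together). Let pF and pP be ID prevalence in non-users who fail and pass, sF and sP the same in recent users, and uF and uP the share of recent users in each stratum.

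- SAP estimate: q·pF + (1 − q)·pP
- All first-time donors: q·[(1 − uF)·pF + uF·sF] + (1 − q)·[(1 − uP)·pP + uP·sP]
- Difference: q·uF·(pF − sF) + (1 − q)·uP·(pP − sP)

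Chance cancellation apart, this is zero only if uF = uP = 0, or if users and non-users have equal prevalence within strata. The documents assume neither.

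**3. Illustrative size.** Suppose the user share is u in both strata and users have r times the non-user prevalence. The difference becomes u × (1 − r) × P, where P is the non-user prevalence. The documents give neither u nor r, so both are assumptions. P is set to the planning ID figure of 41.3% (SAP 2.4; 0.48 × 0.861 = 0.413, the 48% being in the Protocol's Problem Statement). Using it for non-users is also an assumption. Overstatement in percentage points:

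| u | r = 0.25 | r = 0.5 | r = 0.75 | r = 1.25 |
|---|---|---|---|---|
| 2% | 0.6 | 0.4 | 0.2 | −0.2 |
| 5% | 1.5 | 1.0 | 0.5 | −0.5 |
| 10% | 3.1 | 2.1 | 1.0 | −1.0 |
| 20% | 6.2 | 4.1 | 2.1 | −2.1 |

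For example, 0.10 × 0.5 × 0.413 = 0.0207. For IDA (P = 30.7%, r = 0.5) the values at 5%, 10% and 20% use are 0.8, 1.5 and 3.1 points. With the 68.8% ID figure from the Protocol's second unpublished study they are 1.7, 3.4 and 6.9.

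**4. Comparison with the stated margin.** At r = 0.5, the error reaches 5.7 points when u = 0.057/(0.413 × 0.5) = 27.6%. With P = 68.8% it does so at 0.057/(0.688 × 0.5) = 16.6%.

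**5. Relabelling alone is not quite enough.** For non-users, pF and pP are right but q is not. Take a 48% fail rate in non-users, u = 10%, an assumed pF of 0.65, and pP = (0.413 − 0.48 × 0.65)/0.52 = 0.194.

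- User fail rate 30%: q = 0.9 × 0.48 + 0.1 × 0.30 = 0.462. The estimate is off by (0.462 − 0.48) × (0.65 − 0.194) = −0.8 points.
- User fail rate 60%: q = 0.492, and the estimate is off by +0.5 points.

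This residual is small, but it can be removed if exclusions are counted by stratum.

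**The case against.** The best reply is that overall in SAP 7.1 contrasts with within strata. On that reading the weighting does its intended job, undoing the disproportionate approach to donors who fail copper sulphate. Exclusion 1 is stated openly, SAP 3.3 defines the analysis population as eligible and consented participants, and prevalence among donors not recently supplemented is a legitimate quantity. This stands as a defence of the design. It does not rescue the wording: the objective names first-time donors without qualification, and no section narrows the target or plans a sensitivity analysis.

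A second reply is that inclusion 2 requires passing the NBSG questionnaire, which asks about medication, so some users may be absent from both studies. That could shrink the gap. No text says that iron use leads to failure, so it is not shown to close it.

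A reader might also infer more than the documents support:

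- *That a wrong prevalence would misdirect UH3.* The documents tie UH3 to retention, enrolment rates, visit completion and the qualitative findings. None says the prevalence estimate will be used to plan it.
- *That the bias rivals sampling error.* A 6-point error at 15% use needs a 40-point gap (0.15 × 0.40). From 41.3%, that means about 1.3% ID in users if they are less deficient, or 81.3% if more. For IDA at 30.7%, a 40-point drop is impossible.
- *That the NBSG medication question could supply matched weights.* It asks about current medication, not iron in the past month, and a donor may not count a supplement as medication.
- *That exclusion 1 must be lifted for the prevalence study.* SAP 2.4 says that enrolment in that component entails enrolment in the longitudinal study. Admitting donors already known to be ineligible for the trial would probably need a separate consent route.

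**Conclusion.** The point holds as a mismatch between the stated target and what is estimated. Recent iron users are outside the ID/IDA sample, inside the deferral weights and inside the stated target, so the unqualified consistency claim in SAP 7.1 is not supported.

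Size and sign cannot be derived from the documents. Assuming 41.3% ID in non-users and half that in users, the overstatement is about 1, 2 and 4 points at 5%, 10% and 20% use. It is zero if there are no users or prevalences are equal, and negative if users are more often deficient. Under most of the assumptions tried it stays inside the 5.7-point margin; high use combined with a large user/non-user difference, or a much higher base prevalence, can take it past that. The interval covers none of it. This is a minor-to-moderate matter of estimand and wording that affects one secondary objective and leaves the primary trial analysis untouched.

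**What to change.** 1. In SAP 7.1 and in Stratification and Sampling, state the target as first-time donors (or voluntary first-time donors) who have not used iron in the past month, and remove the unqualified overall-population claim.
2. Log the number of otherwise eligible first-time donors excluded for recent iron use, by copper sulphate result, together with the number asked in each stratum. The Protocol already has sites log who is approached, so this adds one field and gives uF and uP.
3. Add a sensitivity analysis with two parts. First, remove users from the deferral weight: q(1 − uF)/[q(1 − uF) + (1 − q)(1 − uP)]. Second, bound the prevalence in all first-time donors with the second formula in step 2 of the working, over a stated range of sF and sP for ID and for IDA.

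The cost is a small logging task, a few lines of SAP text and a narrower stated target. Trial eligibility, treatment and the primary analysis do not change. Measuring ID/IDA in recent users as well is optional, and only if the consent route allows it.

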### **3.2 Withdrawal/follow-up**

A case report form will document participant withdrawal and capture whether the participant initiated the withdrawal, or the withdrawal was administrative. The form will also capture if participants want their data removed from the study database, and the

reason for withdrawal. For participants who initiate withdrawal prior to ascertainment of the primary efficacy endpoint, primary outcome data may be imputed. The withdrawals and how these impact the analysis datasets will be indicated in the CONSORT diagram.

### 3.3 Analysis population

The analysis population for the anaemia deferment study will include all eligible participants, while the analysis population for the ID/IDA study and the trial will include all eligible and consented participants.

### 3.4 Baseline characteristics

Baseline characteristics for those who enrol in the trial will come from information collected on the screening and enrolment forms. The only characteristics captured for those in the anaemia deferment study are age, sex, if the person has previously donated, and the type of donation (i.e., replacement/family or voluntary). For those in the study of ID/IDA information on abnormal peripheral blood film, malaria, haemoglobin, ferritin, and TTI status will also be obtained. Additional information will be available for those in the trial. For the open report, baseline characteristics will be summarized pooled across the two treatment groups and presented separately for those in the anaemia deferment study, the ID/IDA study, and the trial. Note that these study populations are related as follows: everyone in the trial is in the ID/IDA study, and everyone in the ID/IDA study is in the anaemia deferment study. Note that someone who consents to the trial but is found to have levels of haemoglobin that are too low at screening will participate in the ID/IDA study but will not participate in the trial.

For the closed report, baseline characteristics will be summarized by treatment group for the Iron Supplementation Trial.

The following baseline characteristics will be summarized with counts and percentages for binary and categorical variables, medians and quartiles for continuous variables and ordinal variables when available for each of the 3 components of the study.

Demographics:

- Age: summary as continuous variable.
- Sex.
- First-time donation status (Yes or No).
- Number of children (an integer equal or above 0).
- Marital status (6 options).
- Home situation (6 options).
- Main method of travel (private or public).
- Highest level of education completed (7 options).
- Employment category (8 options).
- Number of expensive, durable consumer items (an integer in the range 0-7).
- Ethnic background (6 options).
- Religion (5 options).

Screening laboratory results:

- Haemoglobin concentration.
- Plasma ferritin concentration.

- Malaria test results from a malaria rapid diagnostic test.
- Abnormal peripheral blood film results reported by type of abnormality (i.e., helminthic infection, malaria, neutrophilia, leucocytosis, and lymphocytosis).
- ID present
- IDA present.

Medical History:

- Diagnoses (19 options, select all that apply).

Nutritional History:

- Number of meals yesterday (4 options).
- Vegetarian status (No, Strict, or Partial).

History of Blood Loss:

- Ever given medicine for the treatment of malaria (Yes or No).
- Given medicine for the treatment of malaria within the last 3 months (Yes or No).
- Bleeding piles in the last 3 months (Yes or No).
- Stomach ulcer in the last 3 months (Yes or No).
- Bled from an injury in the last 3 months (Yes or No).
- Surgery in the last 3 months (Yes or No).
- Currently on NSAID painkillers (Yes or No).
- Have sibling(s) with known repeated anaemia (Yes or No).

